				12.0 Error! Bookmark not defined.1
				13.0 Error! Bookmark not defined.15-1
13.1	Error! Bookmaı	k not defined		13.0 End: Bookmark not denned.13-1
_				
13.2	Error! Bookmai			
13.3	Error! Bookmai	k not defined.		
				14.0 1916-1
Append	ices			1

AT2 in Kidney Transplant Page 3 of 22

LIST OF ABBREVIATIONS

ADE Adverse Drug Event
AE Adverse Event
AKI Acute Kidney Injury
ATN Acute Tubular Necrosis

BP Blood Pressure

CrCl Calculated Creatinine Clearance (via Cockcroft Gault equation)

DBP Diastolic Blood Pressure

RAAS Renin-Angiotensin-Aldosterone system

EKG Electrocardiogram

GFR Glomerular Filtration Rate
KDPI Kidney Donor Profile Index
MAP Mean Arterial Blood Pressure
PHI Protected Health Information

SBP Systolic Blood Pressure

HR Heart Rate

SCr Serum Creatinine

UIHHSS University of Illinois Hospital and Health Sciences System
HIPAA Health Insurance Portability and Accountability Act

PHI Protected Health Information

PI Principal Investigator

1.0 PROJECT SUMMARY/ABSTRACT:

The current standard of catecholamine vasopressor management of perioperative hypotension in kidney transplant patients carries significant risks and falls short in many ways. Currently, there is an absence in the scientific literature and research describing the hemodynamic effectiveness and safety of novel pharmacologic agents such as angiotensin II (Giazpreza – Ang II) in perioperative kidney transplant patients. Phase 3 registrational trials have demonstrated the superior safety and efficacy of Ang II (Giapreza) in distributive shock patients compared to traditional vasopressor agents and the novel mechanism of action may provide additional protection in renal transplant patients. The pilot study entails giving informed and consenting kidney transplant recipients Ang II (Giapreza) as their first vasopressor if the need for vasopressors emerge either intraoperatively or postoperatively in kidney transplant recipients. The primary objective is to evaluate the safety and hemodynamic effects of Ang II (Giapreza) in the renal transplant population.

2. BACKGROUND/SCIENTIFIC RATIONALE

The inability to meet blood pressure (BP) goals in the intraoperative and postoperative period of kidney transplantation carries significant consequences, the most serious of which is hypoperfusion to the newly transplanted organ leading to graft failure (Aulakh 2015, Campos 2012, Toth 1998). Following kidney transplant, it is of utmost importance to maintain adequate perfusion to the kidney allograft for optimal function. This adequate perfusion is maintained by the maintenance of adequate systemic blood pressure. Periods of hypotension in the recipient in the intraoperative and postoperative period can have detrimental effects such as acute tubular necrosis (ATN) leading to delayed graft function or even allograft loss (Walsh 2013). In the intraoperative and postoperative setting of kidney transplantation fluid-refractory hypotension (i.e. distributive shock) is primarily reversed by catecholamine vasopressors - phenylephrine, norepinephrine, epinephrine, and dopamine) (Dandan 2019). Unfortunately, animal and human models have demonstrated that the use of catecholamine vasopressors may cause a reduction in renal blood flow, increase in incidence of acute kidney injury (AKI), and worsen clinical outcomes (Busse 2019). It is known that catecholamine vasopressors predominantly vasoconstrict the afferent arteriole of the kidneys and this vasoconstriction can lead to ischemia at the kidney and in a perioperative kidney transplant patient, putting the new allograft at risk for injury and failure by decreasing blood flow to the new allograft. It has been found that perioperative catecholamine usage is associated with decreased urine output after kidney transplantation (Choi 2016), slower normalization of recipient serum creatinine (Day 2014), delayed graft function in recipients (Robert 2010, Day 2014), increased rate of rejection (Choi 2016), increased rate of tachycardias (Robert 2010), increased length of stay, and increased mortality (Choi 2016, Ciapetti 2009). Despite these known risks, no advances have been made in the pharmacologic treatment of intraoperative or perioperative hypotension in decades. As such, there is an urgent need to identify safer and more effective pharmacologic therapies to manage intra- and post-op hypotension/hypoperfusion in the renal transplant population.

Need for the Study

As described above, the current standard of care of catecholamine vasopressors is associated with significant, detrimental adverse effects associated with the mechanism of vasoconstriction of these agents. The reninangiotensin-aldosterone system (RAAS) is an essential hormonal regulator responsible for maintenance of BP via the actions of angiotensin II (AT2). In 2017, the FDA approved pharmacologic angiotensin II (Giapreza – Ang II) for patients with septic shock or distributive shock from other causes (Giapreza prescribing information). Distributive shock is defined as hypotension refractory to appropriate fluid resuscitation, which occurs frequently during the perioperative renal transplant period. After fluid resuscitation is unsuccessful, the use of catecholamine vasopressor agents are the mainstay of therapy for subsequent blood pressure support. As discussed, the narrow therapeutic window and significant risks associated with current vasopressor agents leave a crucial unmet medical need for safer and more effective therapies. In the ATHOS-3 Phase 3 clinical trial Ang II (Giapreza) was shown to have a more optimal pharmacodynamic profile compared to catecholamine vasopressors. It was found that Ang II (Giapreza) more frequently led to mean arterial pressure (MAP) goal attainment than the standard of care (i.e. norepinephrine) and the median duration of MAP goal attainment was 5 minutes for patients on Ang II (Giapreza); an effect that was sustained throughout the study period. Additionally, the usage of concurrent vasopressors was significantly decreased in subjects using Ang II (Giapreza) compared to the standard of care. Lastly, it was found that Ang II (Giapreza) was a safe medication with the most common ADE (> 4% and > 1.5 x placebo) being: thromboembolic events, thrombocytopenia, tachycardia, fungal infection, delirium, acidosis, hyperglycemia, and peripheral ischemia. Despite the commonality of distributive shock in the intraoperative and postoperative period of renal transplants, there are no data available evaluating Ang II (Giapreza) in this population. The more balanced vasoconstriction of AT2 within the kidney vasculature yields a net result of increased filtration fraction and can preserve kidney function (Fehrer 2012). This has been confirmed with animal and clinical human investigations in patients with the highest known risk of developing acute kidney injury (AKI): septic shock (Lankadeva 2018, Tumlin 2018). Thus, it is hypothesized that the use of Ang II (Giapreza) in the intraoperative and perioperative period for renal transplant patients may lead to improved BP management and more optimal safety outcomes compared to the current standard of care conventional catecholamine vasopressors. Therefore, the purpose of this study is to evaluate the safety and efficacy of Ang II (Giapreza) in improving hypoperfusion among renal transplant patients during the critical peri-op period.

The following section is designed to describe the current peri-op processes of renal transplant patients at UI Health in order to clearly delineate how this specific research protocol will deviate from the standard of care.

The normal care process for deceased donor kidney transplants (DDKT) at University of Illinois Hospital and Health Sciences (UIHHSS) includes the following:

PRE-TRANSPLANT

- Patient is end-stage renal disease (ESRD) on dialysis meeting set criteria for kidney transplant
- Patient obtains medical and social clearance for kidney transplant including blood tests (SCr, LFTs, Thyroid studies, CBC w/ diff); Diagnostics: chest X-ray; Cardiac clearance: ECHO, ECG, +/- Stress test, +/- Left heart cath; Cancer screening: colonoscopy, skin CA screening, prostate exam (if applicable), gynecological exam (if applicable); pregnancy screening (if applicable); Surgical clearance; and Nephrology clearance
- Once cleared, patient is listed with our institution and placed on our waitlist
- Patient has yearly check-in visits to re-evaluate if still eligible for transplant and medically able to obtain transplant
- If kidney becomes available, patient is notified to urgently come to either the UIHHSS Surgicenter or Emergency Room to be expeditiously admitted to the OR for their transplant (this time is generally limited to 1-3 hours)
 - It should be noted that time is of extreme value as longer time that passes before implantation of donor kidney has been associated with worse renal outcomes in recipient

DURING TRANSPLANT

- The transplant operation begins.
- If intraoperative hypotension occurs (e.g. SBP < 120 mmHg) the attending surgeon and attending anesthesiologist will:
 - Give blood products first if patient bleeding
 - If not bleeding or hypotensive despite blood products, intravenous fluids will be given
 - If hypotensive despite intravenous fluids then the attending surgeon and attending anesthesiologist will assess for cardiogenic shock and if suspected give inotropes
 - If not in cardiogenic shock and hypotensive despite fluids (+/- inotropes) then catecholamine vasopressors will be given for the treatment of distributive shock.
 - Vasopressor medications will be titrated intraoperatively to achieve goal BP
 - If the patient is unable to be titrated off the catecholamine vasopressors intraoperatively, they will be continued postoperatively in the Intensive Care Unit (ICU) and titrated until the patients' blood pressure is stable without vasopressor support.

 If distributive shock does NOT occur intraoperatively, no continuous infusion catecholamine vasopressors will be initiated

AFTER TRANSPLANT

- If the patient is unable to be titrated off the catecholamine vasopressors intraoperatively, they will be continued postoperatively in the Intensive Care Unit (ICU) and titrated until the patients' blood pressure is stable without vasopressor support.
- If the patient never received continuous infusion vasopressor intraoperatively and postoperative hypotension occurs (e.g. SBP < 120 mmHg) the attending surgeon or ICU team will:
 - Give blood products first if patient bleeding
 - o If not bleeding or hypotensive despite blood products, then intravenous fluids will be given
 - If hypotensive despite intravenous fluids then the attending surgeon and attending anesthesiologist will assess for cardiogenic shock and if suspected give inotropes
 - If not in cardiogenic shock and hypotensive despite fluids (+/- inotropes) then catecholamine vasopressors will be given for the treatment of distributive shock.
 - Vasopressor medications will be titrated postoperatively to achieve goal BP and titrated until the patients' BP is stable without vasopressor support.
- If distributive shock does NOT occur postoperatively, no continuous infusion catecholamine vasopressors will be initiated

3.0 OBJECTIVES/AIMS

Study Objectives

Primary: To evaluate the hemodynamic effectiveness of Ang II (Giapreza) for intraoperative and postoperative hypotension in kidney transplant patients. This will be evaluated by the time to reaching BP goal.

Secondary: To evaluate the safety of Ang II (Giapreza) for intraoperative and postoperative hypotension in kidney transplant patients. This will be evaluated by collecting the incidence of common adverse events (ADE) seen from other Ang II (Giapreza) studies in this patient population.

4.0 ELIGIBILITY

• Eligible patients will include adult patients awaiting DDKT at University of Illinois Hospital and Health Sciences needing a kidney transplant as soon as able.

4.1 Inclusion Criteria

- Adult patients > 18 years of age
- Receiving deceased donor kidney transplant
- Pre-transplant Ejection Fraction (within past 18 months) > 50%
- Intraoperative or postoperative distributive shock (as described above) requiring vasopressor support

4.2 Exclusion Criteria

- Pregnant patients (they would be excluded from receiving a transplant)
- Prisoners
- History of mesenteric ischemia
- History of aortic dissection
- History of abdominal aortic aneurysm

AT2 in Kidney Transplant
Page 8 of 22
Version 2.1
6-1-20

- Allergy to mannitol
- Absolute neutrophil count < 1000 cell/mm3 (within past 18 months)
- Diagnosis of Raynaud's phenomenon, systemic sclerosis or vasospastic disease

4.3 Excluded or Vulnerable Populations

• n/a

5.0 ENROLLMENT

The patients at the top of the adult kidney transplant list awaiting DDKT maintained by UIHHSS Transplant will be used to screen for eligibility. See addendum for Eligibility Checklist. Study personnel will perform the screening. A password protected Microsoft Excel sheet will be provided by the Transplant team at UIHHSS. This sheet will have the MRN for the top patients on the kidney transplant list. If patients are initially eligible via inclusion and exclusion review, they will remain on the password protected Microsoft Excel sheet. If they are not eligible, they will be removed after screening by one of the study personnel. This password protected Microsoft Excel sheet will be maintained on the "H" drive behind the University firewall maintained by the CCTS. It is estimated that 40 subjects will be consented/enrolled in order for 20 patients to receive study drug. Twenty patients are the goal for this study and no more than 20 patients will receive study drug.

All eligible study subjects will receive a Research Letter (see addendum for Research Letter) via the mail. One week after the Research Letter is mailed, the subjects that have not called the primary investigator regarding the study will be called via telephone by study personnel to follow-up and provide any additional information regarding the study. This call is to provide information regarding the study, study enrollment criteria, and answer any questions regarding the study. This call is informational only.

If a kidney transplant is offered to the previously contacted subjects the study personnel will be contacted by the Transplant Coordinator when the kidney transplant is confirmed. Once that subject arrives at UI Health for their transplant, subjects will be approached by study investigators in-person, reminded of the study criteria, have ample time to review study information again and the informed consent document, and will be asked to provide signed consent after the appropriate informed consent process is completed. Researchers participating in the consent process will review the informed consent document (ICD) with the recruited subject in its entirety ensuring the subject understands the research purpose, all risks/benefits and the study components of this research.

Given the urgency surrounding the time course immediately before transplant (as noted in the Background/Rationale section above), it was deemed by the research team that the process of sending a Research Letter and following up via telephone is necessary in order to eliminate delay in the pre-op operations, avoid a coercive environment due to the time dependency of pre-op operations, minimize in-person interactions given the current state of COVID-19, and allow for ample time for information to be exchanged about the study. Additionally, given the lack of routine office visits prior to transplant there is no opportunity to consent these patients in clinic.

6.0 STUDY DESIGN AND PROCEDURES

This will be a single-center, prospective, observational study.

The prospective, observational study will include 20 consecutive patients receiving DDKT requiring intraoperative or postoperative vasopressors to assess the hemodynamic efficacy and safety and efficacy of Ang II (Giapreza).

The care process for this study of Ang II (Giapreza) in deceased donor kidney transplants (DDKT) at University of Illinois Hospital and Health Sciences (UIHHSS) will follow the exact same procedure as described above except (in bold and red):

PRE-TRANSPLANT – n/a DURING TRANSPLANT

- The transplant operation begins.
- If intraoperative hypotension occurs (e.g. SBP < 120 mmHg) the attending surgeon and attending anesthesiologist will:
 - Give blood products first if patient bleeding
 - If not bleeding or hypotensive despite blood products, intravenous fluids will be given
 - If hypotensive despite intravenous fluids then the attending surgeon and attending anesthesiologist will assess for cardiogenic shock and if suspected give inotropes
 - If not in cardiogenic shock and hypotensive despite fluids (+/- inotropes) then Ang II (Giapreza) will be initiated as the first vasopressor given for the treatment of distributive shock.
 - Ang II (Giapreza) will be titrated intraoperative to achieve goal BP.
 - Ang II (Giapreza) will be initiated following the FDA approved dosing in the package insert. This dosing includes a starting dose of 20 nanograms ng/kg/min. Titration will occur every 5 minutes by increments of up to 5 ng/kg/min as needed. During the first 3 hours, the maximum dose will not exceed 80 ng/kg/min. Maintenance dose will n exceed 40 ng/kg/min. Administration through a central venous line will be recommended.
 - If the maximum dose of AT II (Giapreza) is reached (80 ng/kg/min in the first 3 hours or 40 ng/kg/min thereafter), additional vasopressor selection and management will be at the discretion of the attending surgeon and attending anesthesiologist.
 - If additional vasopressors are needed beyond Ang II (Giapreza), all other vasopressors will be titrated off first.
 - If the patient is unable to be titrated off the Ang II (Giapreza) intraoperatively, they will be continued postoperatively in the Intensive Care Unit (ICU) and titrated until the patients' blood pressure is stable without vasopressor support.
- If distributive shock does NOT occur intraoperatively, Ang II (Giapreza) will NOT be initiated.

AFTER TRANSPLANT

- If the patient is unable to be titrated off the Ang II (Giapreza) intraoperatively, they will be continued
 postoperatively in the Intensive Care Unit (ICU) and titrated until the patients' blood pressure is stable
 without vasopressor support.
- If the patient never received Ang II (Giapreza) intraoperatively and postoperative hypotension occurs (e.g. SBP < 120 mmHg) the attending surgeon or ICU team will:
 - Give blood products first if patient bleeding
 - If not bleeding or hypotensive despite blood products, then intravenous fluids will be given

- If hypotensive despite intravenous fluids then the attending surgeon and attending anesthesiologist will assess for cardiogenic shock and if suspected give inotropes
- If not in cardiogenic shock and hypotensive despite fluids (+/- inotropes) then Ang II (Giapreza)
 will be given as the first line vasopressor for the treatment of distributive shock.
- Ang II (Giapreza) will be titrated postoperatively to achieve goal BP and titrated until the patients' blood pressure is stable without vasopressor support.
 - Ang II (Giapreza) will be initiated following the FDA approved dosing in the package insert. This dosing includes a starting dose of 20 nanograms ng/kg/min. Titration will occur every 5 minutes by increments of up to 5 ng/kg/min as needed. During the first 3 hours, the maximum dose will not exceed 80 ng/kg/min. Maintenance dose will n exceed 40 ng/kg/min. Administration through a central venous line will be recommended.
 - If the maximum dose of AT II is reached (80 ng/kg/min in the first 3 hours or 40 ng/kg/min thereafter), additional vasopressor selection and management will be at the discretion of the attending surgeon and attending anesthesiologist.
 - If additional vasopressors are needed beyond Ang II (Giapreza), all other vasopressors will be titrated off first.
 - If at any point the treating physician feels there is a safety concern with the study drug it can be discontinued immediately.
- Ang II (Giapreza) and other vasopressor medications (if applicable) will be titrated
 postoperatively to achieve goal BP and titrated until the patients' BP is stable without
 vasopressor support.
- If distributive shock does NOT occur postoperatively, Ang II (Giapreza) will NOT be initiated

The study drug will be provided by La Jolla Pharmaceuticals for this study but they are not the study sponsor or providing any other financial support. Drug distribution will be managed by the Investigation Drug Service (IDS) at UI Health who has the capacity to retain all of the study drug in appropriate temperature-controlled settings. IDS will be used as this is a novel medication, not yet on formulary at UIHHSS, and this is a research investigation. They will maintain and dispense the medication for each kidney transplant in which subjects have consented in the event that vasopressors are required. Additionally, the medication will be ordered via Cerner/EPIC as a study medication and will be programmed into the Alaris pumps to be dosed via the dosing protocol listed above. Ang II (Giapreza) will not be used outside of the study protocol at our institution and will only be available under the electronic study order. Verifying pharmacists will be in-serviced regarding the study protocol and will be aware that this medication is only available and should be dispensed under the study order and as such not used in other contexts.

FOR STUDIES THAT COLLECT EXISTING OR PROSPECTIVE DATA

Health and laboratory data will be extracted manually from the electronic medical records (i.e. Cerner or Epic) for both arms of the study. Data will be prospectively captured over the course of 3 months after study initiation (i.e. using Ang II (Giapreza) for vasopressor management during kidney transplant) for the pilot. The data will be collected and input into a Redcap database for analysis. Data analysis will be performed using Spss.v25 computer software. Data collection will include the variables below.

Baseline characteristics:

-Age (years of age at the time of transplant)

- -Gender (M/F)
- -Race
- A) White
- B) Black
- C) Asian
- D) Hispanic
- E) Other
- -Weight (kilograms at time of transplant)
- -Height (centimeters at time of transplant)
- -Body mass index (kg/m² at time of transplant)
- -Duration of time on hemodialysis (years)
- -Donor baseline serum creatinine (mg/dL)
- -Warm/cold ischemia time (hours)
- -KDPI
- -Baseline systolic/diastolic/mean arterial pressure (mmHg)
- -Baseline heart rate (HR)
- -Comorbidities
- A) Hypertension
- B) Hyperlipidemia
- C) Heart failure with preserved ejection fraction
- D) Arrhythmias
 - -Atrial fibrillation
 - -Other
- E) Peripheral vascular disease
- F) Coronary artery disease
- G) Pulmonary hypertension
- H) Diabetes
- -Type I
- -Type II

Intraoperative Hemodynamic Data Points:

- -Intraoperative BP (SBP, DBP, MAP) every 5 minutes
- -Intraoperative heart rate every 5 minutes
- -Maximum dose of Ang II (Giapreza) (ng/kg/min)
- -Duration of Ang II (Giapreza) (hours)
- -Number of intraoperative vasopressors (if applicable)
- -Intraoperative agents used in addition to Ang II (Giapreza) (if applicable)
- -Dopamine (Y/N)
- -Norepinephrine (Y/N)
- -Epinephrine (Y/N)
- -Phenylephrine (Y/N)
- -Vasopressin (Y/N)
- -Minimum intraoperative SBP and DBP (mmHg)
- -Minimum intraoperative HR (bpm)

- -Intraoperative volume resuscitation (L)
- -Type of crystalloid and volume: 0.9% NaCl, PlasmaLyte, Lactated Ringers (L)
- -Type of colloids and volume: Albumin, Hydroxyethyl Starch, Mannitol (L)
- -Intraoperative blood product utilization (volume and type of blood products administered)

Post-operative Hemodynamic Data Points:

- -Postoperative BP (SBP, DBP, MAP mmHg) every 1 hour for the first 72 hours or duration of vasopressors (whichever is longer) after transplant
- -Postoperative HR (bpm) every 1 hour for first 72 hours or duration of vasopressors (whichever is longer) after transplant
- -Maximum dose of postoperative Ang II (Giapreza) ng/kg/min
- -Maximum dose of postoperative other vasopressors (in norepinephrine equivalents if applicable)
- -Starting dose of postoperative Ang II (Giapreza) and other vasopressors (in norepinephrine equivalents if applicable)
- -Duration of postoperative vasopressors (hours if applicable)
- -Number of postoperative vasopressors (if applicable)
- -Minimum postoperative BP (SBP, DBP, MAP mmHg) in first 72 hours after transplant (in first 24hrs, second 24hrs, third 24 hrs, and total 72hrs)
- -Minimum postoperative HR (bpm) in first 72 hours after transplant (in first 24hrs, second 24hrs, third 24 hrs, and total 72hrs)
- -Maximum postoperative BP (SBP, DBP, MAP mmHg) in first 72 hours after transplant
- -Maximum postoperative HR (bpm) in first 72 hours after transplant
- -Postoperative agents used:
- -Dopamine
- -Norepinephrine
- -Epinephrine
- -Phenylephrine
- -Vasopressin
- -Postoperative volume resuscitation (L in the first 24hrs, 48hrs, 72hrs)
- -Daily intake volume (milliliters) during ICU admission
- -Daily urine output volume (milliliters) during ICU admission
- -Postoperative blood product utilization (volume and type of blood products administered during ICU admission after operating room)

Post-operative Clinical Data Points:

- -Induction immunosuppression regimen
- -Maintenance immunosuppression regimen
- -First SCr, CrCl, calculated GFR after operating room (mg/dL)
- -Daily SCr, CrCl, calculated GFR after operating room (mg/dL)
- -Average SCr, CrCl, calculated GFR during hospitalization (mg/dL)
- -First serum lactate after operating room (mmol/L)
- -Peak serum lactate after operating room (mmol/L)
- -Duration of elevated (> 2 mmol/L) lactate after operating room (mmol/L)
- -Discharge SCr, CrCl, calculated GFR from hospital (mg/dL)

- -1-month SCr, CrCl, calculated GFR, 3-month SCr, CrCl, calculated GFR
- -Postoperative diuretic utilization (total milligrams of furosemide equivalents)
- -Postoperative midodrine usage (total milligram during hospitalization), duration of usage (days), used upon discharge (Y/N)
- -Postoperative mannitol utilization (Y/N)
- -Baseline serum albumin (mg/dL)
- -Need for renal replacement therapy in the first year after transplantation (Y/N)
- -Mortality during hospital admission for kidney transplant
- -Presumed or definitive allograft rejection rate during hospital admission for kidney transplant
- -Biopsy needed to rule out rejection (Y/N)
- -Calcineurin inhibitor (in tacrolimus equivalents) serum level at 1 week, 1-month, 3-month, 6-month
- -Suspicion for other types of shock (e.g. sepsis, cardiogenic, hemorrhagic as noted in chart documentation)

Safety data points:

Patients will be monitored according to standard monitoring for patients in the peri-operative transplant and collection of ADE will focus on those found in clinical studies using Ang II (Giapreza). The safety endpoints that will be captured will include: incidence of intraoperative arrhythmias for those who receive study drug intraoperatively (confirmed via EKG, flowsheet, or note documentation), incidence of postoperative arrhythmias occurring while receiving study drug postoperatively (confirmed via EKG, flowsheet, or note documentation), incidence of digital or other peripheral/visceral ischemia occurring during hospitalization for kidney transplant (as noted in chart documentation), incidence of venous or arterial thrombosis occurring during the hospitalization for kidney transplant (captured by ultrasound or other diagnostic imaging), incidence of thrombocytopenia while receiving study drug (as defined as platelet count < 50,000), incidence of post-operative fungal infections prior to discharge (as documented by the clinical care team), incidence of delirium while receiving study drug (as documented by the clinical care team), incidence of insulin infusion utilization while receiving study drug, pH values in the ICU at 24hrs, 48hrs, and 72hrs (if available). All of the noted safety variables above are routinely monitored for as part of ICU care.

Data Management

All patients that provide informed consent and receive Ang II (Giapreza) will have their data extracted. These patients will be considered included and associated with an alpha-numeric code that is linked to their medical record number (MRN). This list will be kept in a password protected Excel file on the primary investigator's computer stored on the H drive behind the University firewall on the primary investigator's password protected computer in a locked office. It will be available only to the co-investigators. Lastly, all data collected will not contain PHI and will be stored in Redcap.

All patients that provide informed consent but DO NOT receive Ang II (Giapreza) will be considered a screening failure and NO data will be extracted and they will not be associated with an alpha-numeric code linked to their MRN.

Records retention:

The data will be kept for a minimum of 6 years to meet HIPAA requirements, and after that time the data will be assessed to see if any additional information needs to be collected or any further studies will be conducted. If no further studies will be conducted, the primary investigator will destroy the data at that time.

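### The primary endpoint, time to blood-pressure goal, cannot be computed reproducibly or attributed to Ang II, because the goal, clock start, duration and rescue rules are undefined and no start times are collected

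*Combined protocol and SAP*

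**What the plan says.** Section 3.0 states the primary objective as hemodynamic effectiveness and adds "This will be evaluated by the time to reaching BP goal". Section 6.0 says "Ang II (Giapreza) will be titrated intraoperative to achieve goal BP" and uses the same unspecified goal for postoperative treatment. The only pressure figure is the trigger for action, given as an example: "If intraoperative hypotension occurs (e.g. SBP < 120 mmHg) the attending surgeon and attending anesthesiologist will" take a sequence of steps. It marks hypotension and is not called the goal.

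Another vasopressor may be added once the maximum Ang II dose is reached, at the clinicians' discretion. The data list in Section 6.0 has "Intraoperative BP (SBP, DBP, MAP) every 5 minutes" and "Postoperative BP (SBP, DBP, MAP mmHg) every 1 hour for the first 72 hours or duration of vasopressors (whichever is longer) after transplant". For intraoperative added agents it records the number and a yes/no per drug. It lists maximum doses and durations, but no start time for Ang II or any added agent, no goal and no time-to-goal field.

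Section 9.0 assigns a Student t-test to continuous data and names no time-to-event method. Section 1.0 states the primary objective differently: "The primary objective is to evaluate the safety and hemodynamic effects of Ang II (Giapreza) in the renal transplant population". Section 3.0 makes safety secondary.

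**The concern.** This is the study's only named efficacy measure, in 20 treated patients, open label, with no defined comparator. Two careful analysts given the same charts could report different results, because each would have to choose the goal, the pressure component, the start of the clock, whether one reading is enough, and what to do with patients who were rescued or never reached goal. All of these could be settled after the data are seen. With 20 patients, each reclassified patient moves the proportion attaining goal by 1/20 = 5 percentage points.

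The component matters for interpretation too. Section 2 cites a median of 5 minutes to a mean arterial pressure goal in the earlier phase 3 trial, while this protocol's trigger is systolic. A reader could not tell whether the two times are comparable.

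**Working it through.** **The plan's own size figure.** The protocol expects 40 consented subjects for 20 treated, at about 50% vasopressor use: 20 / 0.50 = 40, which reproduces. There is no power, alpha or effect size to check, and this point does not depend on the 40.

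**Effect of the undefined goal.** Assume, for illustration, that systolic pressure rises linearly from 100 mmHg at 1 mmHg per minute. Time to goal = (goal - 100) / 1:

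| Goal (mmHg) | True time (min) | On 5-min grid | On hourly grid |
|---|---|---|---|
| 110 | 10 | 10 | 60 |
| 120 | 20 | 20 | 60 |
| 130 | 30 | 30 | 60 |
| 140 | 40 | 40 | 60 |

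The choice of goal alone changes the intraoperative result fourfold. On hourly postoperative readings all four cases are recorded as 60 minutes, so that grid lengthens recorded times.

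**When rescue can matter.** Section 6.0 gives a start of 20 ng/kg/min, steps of up to 5 every 5 minutes, and a maximum of 80 in the first 3 hours. The minimum time to maximum is (80 - 20) / 5 = 12 steps, and 12 x 5 = 60 minutes. If this is followed, a vasopressor added at maximum dose in the first 3 hours can affect only attainment after about 60 minutes. A median is untouched if more than half the patients (11 or more of 20) reach goal on Ang II alone before then. The mean and the proportion attaining can still change.

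**Single versus sustained readings.** Assumptions, none from the documents: no change in true pressure, a constant gap below goal, reading SD 8 mmHg, 12 five-minute readings in an hour, 200,000 simulated patients. Probability of falsely meeting the goal:

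| Gap (mmHg) | Lag-1 correlation | One reading | Three consecutive |
|---|---|---|---|
| 5 | 0 / 0.5 / 0.8 | 0.975 / 0.906 / 0.735 | 0.139 / 0.333 / 0.395 |
| 10 | 0 / 0.5 / 0.8 | 0.739 / 0.616 / 0.433 | 0.011 / 0.082 / 0.149 |
| 15 | 0 / 0.5 / 0.8 | 0.310 / 0.259 / 0.173 | 0.0003 / 0.011 / 0.036 |

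Check at zero correlation: 1 - Φ(gap/8)^12. For a 10 mmHg gap, Φ(1.25) = 0.8944 and 1 - 0.8944^12 = 0.74, which agrees. Correlation lowers the one-reading figure and generally raises the three-reading figure. Letting SD run from 5 to 10 widens the ranges to 1-99% and 0-46%.

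**Attribution.** Separating attainment on Ang II alone from attainment after rescue requires the order of three times: Ang II start, goal reached, added agent start. The data list provides dated pressures but neither start time.

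**The case against.** A reader might infer that the plan accepts one noisy reading and credits Ang II with goals reached after rescue. It states neither rule. It is silent, and silence permits these readings without adopting them. First touch is the natural sense of reaching a goal, but it is not written down.

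A reader might also infer that the result will be biased toward apparent success. The documents do not support that. There is no success threshold or hypothesis, hourly postoperative readings make Ang II look slower, and rescue given as specified comes no earlier than about 60 minutes. The direction is uncertain.

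Other limits also stand. The simulation inputs are assumed, and a three-reading rule is no cure for patients just below goal, with 14-40% false attainment at a 5 mmHg gap. A rule based on 5-minute readings cannot be applied to hourly postoperative data. The 120 mmHg figure is only an example of hypotension; if the team titrates to another target, an endpoint built on 120 would not measure that target. These limits shape the remedy. They do not supply the missing definition.

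**Conclusion.** The concern holds as a defect of definition and data capture. The primary endpoint lacks a goal value, pressure component, time zero, duration, rescue rule and non-attainment rule, and the listed fields cannot separate response to Ang II from response to combined treatment. The tests in Section 9.0 do not fill the gap. This rests on the documents alone.

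The size of the effect on results is not established. Single-reading or post-rescue attainment would favour Ang II, and hourly sampling works the other way. The limited reach of rescue (later attainment, the mean and the proportion, possibly not the median) assumes the stated titration is followed. The false-attainment ranges, about 17-98% for one reading and 0.03-40% for three, are illustrative at SD 8 mmHg, gaps of 5-15 mmHg and correlation 0 to 0.8. They support a sustained-reading rule but do not forecast this trial. The plan should be changed before enrolment, while start times can still be collected prospectively.

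**What to change.** For analysis only, leaving titration targets to the treating team:

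1. Before enrolment, fix one analysis goal and pressure component. This could be the protocol's own systolic 120 mmHg figure, or the team's goal recorded before infusion start. Report the other as a sensitivity analysis.
2. Time from the start of the Ang II infusion. Add the start times of Ang II and of each added vasopressor to the data list.
3. Require sustained attainment, with the number of consecutive 5-minute readings stated in advance for intraoperative data. For postoperative starts, use charted readings taken during titration if available; otherwise report these patients separately as interval-censored on the hourly grid. Say which rule applies to patients who leave the operating room before attainment.
4. Treat another vasopressor started before attainment as a competing event, censor the remaining non-attainers at a stated time, and report cumulative incidence instead of a t-test.
5. State the same primary objective in Sections 1.0 and 3.0.

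The cost is protocol wording and a few more chart-extracted time fields. Fewer patients will count as attaining goal. Postoperative starts may have to be reported with coarser timing if only hourly readings exist.
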